### 7.4.2 Adverse Events

Adverse events (AEs) will be recorded from the time of randomization through 35 days. Symptoms/side-effects described previously will generally not be counted as AEs, as they will be reported separately. Serious adverse events (SAEs), unexpected medically attended events, and new chronic illnesses will be reported from randomization through one year after last study dose. Adverse events will be coded using the Medical Dictionary for Regulatory Activities (MedDRA), version 14.0.

**All Adverse Events** Summaries of incidence rates (frequencies and percentages), intensity, and relationship to study of individual AEs by System Organ Class and Preferred Term (MedDRA) will be prepared. All AEs beginning after randomization but before discharge will be included. Basic summaries by assigned groups will be prepared. The DSMB may request to see more detailed tables. The occurrence of any adverse event will be considered as a dichotomous outcome and will be compared between groups using a Mantel-Haenszel test, stratified by clinical center and duration of symptoms.

**Serious Adverse Events/Deaths** SAEs/Deaths will be reported separately in a similar fashion to the more general AE reports. In addition, narratives will be available for each event.

## 7.5 Analysis of Tertiary Outcomes

Tertiary outcomes will be analyzed in a manner similar to the primary and secondary outcomes. Dichotomous outcomes will be compared between groups using the Mantel-Haenszel test, while continuous outcomes will be compared using the Van Elteren test. Both types of tests will be stratified by the randomization stratification factors: clinical center and duration of symptoms.

## 7.6 Analysis of Subgroups

There are 3 subgroup factors prespecified for formal analysis in this trial:

1. Age (under 1 year versus 1 and older)
2. Antibiotic useage during the 14 days prior to ED visit,
3. Infectious agent: virus, bacteria, parasite, or other/unidentified.

Rates of the primary study outcome will be reported by treatment arm for all prespecified subgroups. Secondary outcomes will also be reported by arm for all subgroups.

A “subgroup” effect will be declared to be significant only if the interaction between assigned treatment and the subgroup factor is significant in the appropriate statistical model testing for each particular interaction, at a significance level of  $0.05/3 = 0.017$ . These results must still be viewed with caution, given the number of outcomes. For the primary outcome, and other binary outcomes, logistic regression models will be used with a main effect for treatment, a main effect for the subgroup variable of interest, and an interaction between the subgroup variable of interest and the treatment. Interactions for continuous outcomes will be evaluated in a similar manner, using linear regression models.

## Abbreviations

Abbreviation	Definition
DCC	Data Coordinating Center
CRF	Case Report Form
DSMB	Data and Safety Monitoring Board
ITT	Intent-To-Treat
MCID	Minimal Clinically-Important Difference
MVS	Modified Vesikari Score
PECARN	Pediatric Emergency Care Applied Research Network
PP	Per-Protocol
(S)AE	(Serious) Adverse Event
SAFETY	Safety Population
SAP	Statistical Analysis Plan

# 1 Preface

## 1.1 Purpose of SAP

This Statistical Analysis Plan (SAP) describes the planned analysis and reporting for the PECARN Protocol: Impact of Emergency Department Probiotic Treatment of Pediatric Gastroenteritis (Probiotics Study).

The purpose of this study is to determine if probiotic administration reduces the severity of acute gastroenteritis episodes in children aged 3 to 48 months. The study is a randomized, placebo-controlled trial with a parallel-group design.

The structure and content of this SAP provides sufficient detail to meet the requirements and standards set by the PECARN Data Coordinating Center (DCC). All work planned and reported for this SAP will follow guidelines for statistical practice published by the American Statistical Association [2].

## 1.2 Auxiliary/Other Documents

The following documents were reviewed in preparation of this SAP:

- PECARN Protocol: Impact of Emergency Department Probiotic Treatment of Pediatric Gastroenteritis (Probiotics Study).
- Case Report Forms (CRFs) for the Probiotics protocol

The reader of this SAP is encouraged to read the protocol for details on the conduct of this study, and the operational aspects of clinical assessments.

The purpose of this SAP is to outline the planned analyses to be completed for the Probiotics trial. The planned analyses identified in this SAP will be included in future study abstracts and manuscripts. Also, exploratory analyses not necessarily identified in this SAP may be performed. Any post hoc, or unplanned, analyses not explicitly identified in this SAP will be clearly identified as such in any published reports from this study.

It is possible that, due to updates or identification of errors in specific statistical software discussed in this SAP, the exact technical specifications for carrying out a given analysis may be modified. This is considered acceptable as long as the original, prespecified statistical analysis approach is completely followed in the revised technical specifications.

# 2 Study Objectives and Outcomes

## 2.1 Study Objectives

### 2.1.1 Primary Objectives

The primary objectives of the Probiotics trial are:

1. to test the hypothesis that, in children with acute gastroenteritis, probiotic administration in the emergency department will decrease the likelihood of moderate-severe disease, defined by a validated Modified Vesikari Score (MVS)  $\geq 9$ , compared to placebo.
2. to test the hypothesis that, in children with acute gastroenteritis, probiotic administration will not be associated with serious adverse events, and will have a similar rate of side effects (e.g., bloating, fever, abdominal distention) as compared to placebo-treated children.

## 2.2 Study Outcomes

### 2.2.1 Primary Outcome

The primary outcome is the presence of moderate-severe acute gastroenteritis, as defined by a total post-enrollment Modified Vesikari Score (MVS)  $\geq 9$  during the 2-week follow-up period.

### 2.2.2 Safety Outcomes

Safety outcomes are:

1. The occurrence of invasive disease (including meningitis and bacteremia) from *Lactobacillus rhamnosus*.
2. Occurrence of side effects: bloating, gas, intestinal rumbling, diarrhea, blood in stool, abdominal pain, abdominal cramps, nausea, vomiting, loss of appetite, heartburn, constipation, skin rash, diaper rash, fever, nasal congestion, runny nose, sore throat, cough, headache, muscle aches, chills, weakness.

### 2.2.3 Secondary Outcomes

Secondary outcomes are:

1. Time to last watery stool as reported during daily surveys.
2. Time to last vomiting episode. Vomiting duration is only evaluated in children who vomited  $\geq 3$  times during the 24 hours prior to the emergency department visit.
3. Return visits for unscheduled care to a healthcare provider related to vomiting, diarrhea, dehydration, fever, or fluid refusal, within 2 weeks of the index visit.
4. Days of daycare missed by subjects who attend daycare.
5. Days of work missed by caregivers who work outside of the home.

## 6. Household transmission rate.

In addition to the primary analysis, MVS will be analyzed in secondary analyses for confirmatory purposes as:

1. a numeric variable (i.e., actual MVS, rather than dichotomized)

### 2.2.4 Tertiary Outcomes

Tertiary outcomes are:

1. Emergency department acute gastroenteritis-related visits
2. Intravenous rehydration
3. Hospitalization
4. Total number of diarrheal stools
5. Total number of vomiting episodes
6. Adherence to oral medication (defined as  $\geq 7$  out of 10 doses)

In the event that efficacy of the probiotic is demonstrated, cost will also be analyzed (cost-effectiveness).

## 2.3 Covariates

Although randomization should result in approximate balance between treatment groups with respect to critical baseline variables affecting the outcomes, additional exploratory analyses will be conducted to assess the effects of treatment after adjusting for baseline covariates in models for each outcome. The covariates considered are:

- baseline MVS (actual score),
- duration of symptoms prior to enrollment (<48 hours vs. 48 hours or more),
- age,
- gender,
- clinical center,
- breast-feeding status,
- antibiotic useage during the 14 days prior to ED visit,

- infective agent at baseline (e.g., norovirus, rotavirus),
- hydration assessment (Gorelick dehydration score),
- need for hospitalization from initial ED visit,

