## Initial Study Drug Administration

Clinical staff in the emergency department will administer the first dose of study drug by sprinkling the capsule's contents into 20-30 mL of room temperature non-carbonated liquid. Capsule contents may also be sprinkled into 1 tablespoon of applesauce as an alternative to liquid. Oral fluid therapy will be encouraged according to sites' existing clinical guidelines. At discharge, parents will also be provided with clinical instructions concerning what and how much fluid to drink, criteria for returning to the emergency department or seeing their physician, and other standardized discharge instructions for acute gastroenteritis. Study research coordinators will provide the parents with instructions concerning study drug administration at home, completion of study forms, and a letter for their pediatrician that explains the study. The importance of administering all doses dispensed and the need to communicate with the study team on a daily basis until symptoms resolve will be stressed.

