The primary efficacy endpoint (the presence of moderate or severe disease, as defined by a total Modified Vesikari Score  $\geq 9$  during the 2 week follow-up period) will be limited to symptoms and outcomes that occur after randomization. If a patient's symptoms of vomiting and diarrhea stop during the same 24 hours, and then recur, that is not included in the post-enrollment score since that will be considered a *new* illness. In the original score, severe disease was defined as  $\geq 11$  and moderate as  $\geq 9$ . In our derivation and validation pilot studies, construct validity was demonstrated and validated by using scores of  $\geq 9$  to define moderate and  $\geq 11$  to define severe disease. These cut-points were associated with significant increases in other measures of disease severity such as degree of dehydration, likelihood of admission and daycare ( $p = 0.01$ )

and parental work absenteeism ( $p < 0.001$ ).

The proportion of children with moderate-to-severe disease (i.e. Modified Vesikari Score  $\geq 9$ ), the primary outcome, will be analyzed by comparing proportions utilizing a Mantel-Haenszel test, stratified by participating center and by duration of symptoms at enrollment. Significance for this primary outcome measure will be set at 0.05. Secondary analyses of the primary outcome will use logistic regression methods to adjust for covariates that may be imbalanced between groups, (e.g. age, pre-enrollment Modified Vesikari Score, hydration assessment, need for hospitalization at index visit). We will also analyze the outcome using Modified Vesikari Score as a continuous variable through a stratified Wilcoxon rank-sum test and compare the results with the primary analysis.

**Specific Aim 2.** Determine the safety and side effect profiles of *Lactobacillus rhamnosus* GG, ATCC 53103 (LGG) in children presenting to the emergency department with acute gastroenteritis.

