## 3 Study Design and Methods

### 3.1 Overall Study Design

The Probiotics trial has a parallel group design with a placebo control. We will not describe specifics about the active agent or placebo here, as these are contained in the protocol. We will refer to the two trial arms as Active and Placebo. Study participants will be randomized to Active or Placebo, each having equal allocation. Treatment with the assigned therapy is to commence immediately following randomization. The primary analysis will be performed on an intention-to-treat basis. We will also use an enrichment design, possibly modifying the eligibility criteria of the trial based on interim results.

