- 4. Diarrhea duration.** This is calculated as the time between randomization and the last diarrhea episode. When diarrhea is reported to have stopped on one survey, and started again on a later survey, but prior to all symptoms (i.e., vomiting in this case) stopping, the durations of diarrhea episodes are summed. The first diarrhea episode would be calculated from randomization date/time until the first diarrhea stop date/time. Subsequent episodes would be calculated from the beginning (noon) of the survey day on which diarrhea reportedly returned until the next diarrhea stop date/time. In cases where diarrhea stop date/times are not in sync with the expected survey dates, we assume the date/times to be correct as long as a daily duration is no more than 84 hours (i.e., more than 3.5 days) late. Otherwise, we assume the dates are erroneous, and use the expected dates instead of the reported dates. For example, if the stop date on survey 5 should be Jan 5, but is reportedly Feb 5, we would use Jan 5. If the reported date was Jan 8, we would assume that some surveys were skipped, and

use Jan 8. If any duration is less than 0, we use 0 hours. This will happen if diarrhea stops at any time prior to randomization.

5. **Vomiting duration.** This component will be calculated using exactly the same procedure described for diarrhea when vomiting is present at randomization. If vomiting is not present at randomization and never occurs, vomiting duration will be 0. If vomiting starts after randomization, the start time will be the start time (noon) of the first daily survey where vomiting is present.
6. **Unscheduled healthcare visit.** Presence of an unscheduled healthcare visit will be collected on the survey and will be classified as “none”, “primary care”, or “emergency department”.
7. **Treatment.** Treatment will be classified as “none”, “rehydration”, or “hospital admission”. If the patient is admitted directly following their enrollment ED visit and that admission stay is longer than 48 hours, it will be counted as treatment in the post enrollment MVS. If the patient’s enrollment admission stay was less than 48 hours, it will not be counted as “treatment”. The same logic will be used for “rehydration” during the enrollment ED visit (and admission stay, if admitted).

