### 7.2.1 Multiple Imputation

When the primary outcome is unable to be derived due to missing data, multiple imputation will be used. This method will be applied to the components of the overall MVS: Diarrhea duration, Maximum number of diarrheal stools/24 hours, Vomiting duration, Maximum number of vomiting episodes/24 hours, Maximum fever, Unscheduled ED visit, Unscheduled Primary Care Visit, Rehydration, and Hospital Admission. In the case where no MVS outcome data are available, the subject will not be included in imputations and the outcomes will remain missing.

**Sequential Regression Multivariate Imputation Models** We will use logistic regression methods to model unscheduled ED visit, Unscheduled Primary Care Visit, Rehydration, and Hospital Admission. We will use Poisson or linear regression methods to model Diarrhea duration, Maximum number of diarrheal stools/24 hours, Vomiting duration, Maximum number of vomiting episodes/24 hours, and Maximum fever. For all models, we will use forward stepwise variable selection to select predictors.

**Variables to include in imputation models** *Stratum:* Stratify models using treatment assigned

*Minimum and maximum possible values will be computed and used as bounds for imputing MVS components:* Diarrhea duration, Maximum number of diarrheal stools/24 hours, Vomiting duration, Maximum number of vomiting episodes/24 hours, Maximum fever

*General model variables:* age, gender, breast-feeding status, hospital/site

*Baseline model variables:* duration of symptoms prior to enrollment, diarrhea duration, maximum number of diarrheal stools/24 hours, vomiting duration, maximum number of vomiting episodes/24 hours, maximum fever, dehydration status, antibiotics use, Number in household, number infected in household

*Post-randomization model variables:* Time to symptom resolution, ED disposition, primary care visits, Emergency department visits, hospital admissions, daycare days missed, work days missed, antibiotic use, invasive LGG disease, bloating, gas, intestinal rumbling, blood in stool, abdominal cramps, nausea, loss of appetite, heartburn, constipation, skin rash, muscle aches, sore throat, cough, headache, chills, weakness, runny nose, number infected in household

*Minimum and maximum possible values will also be used for imputing the following:* Daycare Days Missed, Work Days Missed, number infected in household

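### Index-visit hospitalization is listed as a baseline covariate, but the plan elsewhere treats it as post-randomization, so the adjusted models may absorb part of any treatment effect acting through index admission.

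*Combined protocol and SAP*

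**What the plan says.** SAP 2.3 states that "additional exploratory analyses will be conducted to assess the effects of treatment after adjusting for baseline covariates in models for each outcome", and the list that follows includes "need for hospitalization from initial ED visit". SAP 7.1 puts the same item in the table of demographic and pre-treatment characteristics. SAP 7.2.2 sends the section 2.3 covariates into a logistic model for MVS of 9 or more and a linear model for the continuous score. Protocol 5.1 describes secondary logistic models that adjust for covariates that might be imbalanced, and its examples include "hydration assessment, need for hospitalization at index visit".

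On timing, SAP 3.1 says "Treatment with the assigned therapy is to commence immediately following randomization". Protocol 4.2 says "Clinical staff in the emergency department will administer the first dose of study drug". SAP 7.2.1 lists, under the post-randomization variables of the imputation models, "Time to symptom resolution, ED disposition, primary care visits".

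On the outcome, SAP 7.2 item 7 says that if a child is admitted directly from the enrollment visit and "that admission stay is longer than 48 hours, it will be counted as treatment in the post enrollment MVS". Table 1 gives hospital admission 2 points. A shorter index stay does not score.

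**The concern.** A baseline covariate should be fixed before treatment can act on it. Here the plan gives one event two roles: a predictor describing the child at entry and, for longer stays, part of the outcome being predicted. If the probiotic lowered index admission, the adjusted models would hold that benefit constant and estimate only what remained.

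The protocol's rationale adds to this. It adjusts for covariates that look imbalanced, so a difference in admission caused by treatment would be handled as chance imbalance. It would read the same way in the SAP 7.1 table. The protocol calls these models secondary analyses of the primary outcome, so they are likely to be read beside the primary result.

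There is also a smaller gap. The adjusted models are planned for every outcome, and SAP 2.2.4 lists hospitalization as a tertiary outcome without saying whether the index stay counts. If it does, that model would regress hospitalization partly on itself.

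**Working it through.** **Passages side by side.**

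- Baseline reading: SAP 2.3, SAP 7.1 and protocol 5.1.
- Post-randomization reading: SAP 3.1 with protocol 4.2 (dosing starts in the ED at randomization), SAP 7.2.1 (ED disposition) and SAP 7.2 item 7 (long index stays score). Protocol 5.1 also confines the post-enrollment score to symptoms and outcomes after randomization. By that rule, an index stay that scores is a post-randomization event.
- Not stated anywhere: whether the admission decision is made or recorded before randomization.

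**The plan's own figure.** SAP 3.3 gives 670 for 25% vs 15%, two-sided 0.05 and 90% power. The pooled-variance formula without continuity correction gives

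n per arm = [1.960·√(2·0.20·0.80) + 1.282·√(0.25·0.75 + 0.15·0.85)]² / 0.10² = 334.2, rounded up to 335, so 670 in total.

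The covariate does not enter this calculation or the Mantel-Haenszel test.

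**How much adjustment could remove.** Let h_P and h_A be the index admission proportions on placebo and active, and q₁ the event rate among admitted children, taken as equal in both arms. The event rates among children not admitted are then set so that the overall rates are 25% and 15%:

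- q₀P = (0.25 − h_P·q₁)/(1 − h_P)
- q₀A = (0.15 − h_A·q₁)/(1 − h_A)

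Standardizing over the pooled admission proportion h̄ = (h_P + h_A)/2:

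- adjusted risk difference = (1 − h̄)(q₀P − q₀A)
- amount removed = 0.10 − adjusted = (h_P − h_A)·[q₁ − (q₀P + q₀A)/2]

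The removed amount is zero when h_P = h_A.

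Example: h_P = 5%, h_A = 2.5%, q₁ = 60%. Then q₀P = 0.22/0.95 = 0.2316, q₀A = 0.135/0.975 = 0.1385 and h̄ = 0.0375. The adjusted difference is 0.9625 × 0.0931 = 0.0896, so 10% of the effect is removed.

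Adjusted risk difference, with the share of the 10-point effect removed:

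| Index admission, placebo vs active | q₁ = 40% | q₁ = 60% | q₁ = 80% |
|---|---|---|---|
| 5% vs 5% | 0.100 (0%) | 0.100 (0%) | 0.100 (0%) |
| 5% vs 4% | 0.098 (2%) | 0.096 (4%) | 0.094 (6%) |
| 5% vs 2.5% | 0.095 (5%) | 0.090 (10%) | 0.084 (16%) |
| 5% vs about 0% | 0.090 (10%) | 0.080 (20%) | 0.069 (31%) |
| 10% vs 5% | 0.089 (11%) | 0.078 (22%) | 0.068 (32%) |

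The 25%, 15% and 10-point figures are from SAP 3.3. The 5% is suggested by protocol 4.2, which expects fewer than 5% of enrolled children to be hospitalized but does not separate index from later admission. The other admission rates, the arm differences and q₁ are assumptions.

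**Odds-ratio scale.** The planned model for the binary outcome is logistic. The unadjusted odds ratio is 0.529. At 5% vs 2.5% the adjusted value is 0.543, 0.552 and 0.556 for the three values of q₁. At 5% vs 5%, where nothing is removed on the risk-difference scale, it is still 0.525, 0.510 and 0.483. A change in the odds ratio after adjustment is therefore not a clean measure of the loss, and the risk-difference figures are the better guide.

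**The case against.** The strongest reply is that the plan does not establish the timing. The covariate is the need for hospitalization, which could be known when the child is enrolled, and the documents do not say when the decision is taken. ED disposition in SAP 7.2.1 sits beside later care and is not tied explicitly to the index visit. Overlap with the outcome is partial: only stays over 48 hours score, while the covariate is any index admission, so an effect that merely shortened stays would not be absorbed. The models concerned are exploratory in SAP 2.3, and protocol 5.1 offers the variable only as an example. The SAP's named secondary logistic model adjusts for baseline MVS alone.

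All of this stands as a limit on the point. It does not remove it: the plan labels the variable baseline without fixing its timing, starts dosing in the ED, and lets long index stays score in an outcome confined to post-randomization events.

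A reader might infer that the adjusted models do remove part of the treatment effect. The documents do not support that. It would require the probiotic to change index admission, possibly after a single ED dose, and no section claims this. The prior effects cited in protocol 2.1 concern diarrhea duration and stool frequency. A reader might also infer that the covariate has nothing to offer. That is unsupported too, since the admission decision may carry severity information beyond baseline MVS and the dehydration score.

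**Conclusion.** The point holds in conditional form. The baseline label in SAP 2.3 and 7.1 is at odds with the plan's other sections, and the secondary and exploratory adjusted models may absorb part of any effect that runs through index admission. With 5% index admission on placebo and q₁ of 40% to 80%, the share of a 10-point effect at risk is nil if admission is unchanged, about 2% to 6% if it falls to 4%, and about 5% to 16% if it falls to 2.5%. Larger losses need index admission to be almost eliminated or to be commoner than the protocol expects. These sizes rest on assumed rates. The primary Mantel-Haenszel test, its alpha and its power do not depend on this variable. The change is worth making because it is cheap and removes an avoidable ambiguity, but no primary conclusion depends on it.

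**What to change.** 1. Delete index hospitalization from the covariate list in SAP 2.3 and from the examples in protocol 5.1.
2. Take it out of the pre-treatment table in SAP 7.1 and report it by arm as a post-randomization variable.
3. Keep baseline MVS and the Gorelick dehydration score as the severity covariates.
4. Retain it as a covariate only if it is redefined as a disposition decision recorded before randomization, with that timing written into the SAP.
5. State which ED visit the disposition in SAP 7.2.1 refers to, and whether the tertiary hospitalization outcome includes the index stay.

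The cost is a text edit and one fewer model term, with no new data. The one downside is that some severity information carried by the admission decision may be lost from the adjusted models.
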